### 10.3.3.1 Clinical Laboratory Safety Assessments

#### 10.3.3.1.1 Clinical Laboratory Tests to be Performed

Samples for the following laboratory tests will be collected at the time points indicated in the Schedule of Events ([Table 2-1](#)).

Complete blood count: hemoglobin, hematocrit, red blood cell (RBC) count, red cell distribution width (RDW), mean corpuscular hemoglobin (MCH), mean corpuscular hemoglobin concentration (MCHC), mean corpuscular volume (MCV), platelet count (or estimate), white blood cell count including differential (percentage and absolute: basophils, eosinophils, lymphocytes, monocytes, neutrophils)

Blood chemistry: albumin, creatinine, blood urea nitrogen (BUN), eGFR, total bilirubin, total protein, alkaline phosphatase, alanine aminotransferase, aspartate

aminotransferase, lactate dehydrogenase, gamma-glutamyl transferase, lipase, lactate, blood glucose

Coagulation: international normalized ratio (INR), prothrombin time, partial thromboplastin time, fibrinogen

Urinalysis: pH, specific gravity, blood, glucose, protein, ketones

Other: sPLA2 enzyme activity and biomarkers (cardiac troponin, C-reactive protein [CRP], and ferritin)

Serum pregnancy test: for participants of childbearing potential only

Routine laboratory specimens will be analyzed at local laboratories, PK and sPLA2 samples will be analyzed by a central laboratory. Specimens must be prepared for analysis according to the instructions provided in the study laboratory manual before shipment to the central laboratory.

#### **10.3.3.1.2 Evaluation of Clinical Laboratory Values**

Each local laboratory will provide the normal ranges of values for the clinical laboratory assessments in this study, and the local ranges will be regarded as the reference ranges on which decisions will be made by each investigator.

If a laboratory value is out of the reference range, it is not necessarily clinically relevant. The investigator must evaluate the out-of-range values and record his or her assessment of the clinical relevance in the appropriate eCRF.

All clinical laboratory values that in the investigator's opinion show clinically relevant or pathological changes during or after termination of treatment must be reported as AEs and followed, as described in [Section 11.2](#).

#### **10.3.3.2 Clinical Examinations**

##### **10.3.3.2.1 Vital Signs and Peripheral Oxygen Saturation (SpO2)**

Vital signs (including body temperature) and peripheral oxygen saturation (SpO2) will be assessed at the timepoints indicated in the Schedule of Events ([Table 2-1](#)) per institutional practice.

If the participant has multiple vital sign or SpO2 assessments on a given day, an assessment measured between 6 am-noon should be recorded in the eCRF, if possible, for consistency.

##### **10.3.3.2.2 Twelve-lead Electrocardiogram**

A standard 12-lead electrocardiogram (ECG) will be performed at the timepoints indicated in the Schedule of Events ([Table 2-1](#)) per institutional practice. All ECG recordings will be identified with the participant identification, date, and time of the recording and will be attached to the participant's eCRF.

##### **10.3.3.2.3 Physical Examination**

A physical examination will be performed at the timepoints indicated in the Schedule of Events ([Table 2-1](#)) per institutional practice.

#### **10.3.3.2.4 Neurological Assessment**

A neurological assessment will be performed at the timepoints indicated in the Schedule of Events (Table 2-1) per institutional practice.

#### **10.3.3.3 Adverse Events**

The definitions and management of AEs, and any special considerations for AEs, are provided in [Section 11](#).

## 11. ADVERSE EVENTS

### 11.1. Definitions

#### 11.1.1 Adverse Events

An AE is defined as any untoward medical occurrence in a patient or clinical investigation participant administered an investigational product that does not necessarily have a causal relationship with this treatment. An AE can therefore be any unfavorable and unintended sign (including an abnormal laboratory finding, physical examination finding, or neurological finding), symptom, or disease temporally associated with the use of a medicinal product, whether or not related to the medicinal product.

Pre-existing diseases or conditions will not be considered AEs unless there is an increase in the frequency or severity or a change in the quality of the disease or condition. Worsening of a pre-existing condition is considered an AE. Worsening or progression of the COVID-19 disease under study will not automatically be considered an AE unless the investigator believes that the progression is related to study drug. In that case, the worsening or progression of COVID-19 disease under study will be reported as an AE / SAE as appropriate.

Events that occur in participants treated with placebo, or during treatment-free periods of the study, are also considered AEs.

#### 11.1.2 Unexpected Adverse Event

An expected AE is one for which the nature or severity is consistent with the known AE profile of the product. For a pre-approval test product, the known information is contained in the IB. An unexpected adverse event is one for which the nature or severity is not consistent with the IB. All AEs whether expected or unexpected will be recorded.

#### 11.1.3 Serious Adverse Events

A serious adverse event (SAE) is any untoward medical occurrence that:

- results in death
- is life-threatening

NOTE: The term “life-threatening” in the definition of “serious” refers to an event in which the patient was at risk of death at the time of the event; it does not refer to an event that hypothetically might have caused death if it were more severe.

- requires inpatient hospitalization or prolongation of existing hospitalization  
NOTE: An elective hospital admission to treat a condition present before exposure to the IP, or a hospital admission for a diagnostic evaluation of an AE, does not qualify the condition or event as an SAE.
- results in persistent or significant disability/incapacity
- is a congenital anomaly in an infant born to a mother who was exposed to the IP during pregnancy (a newly diagnosed pregnancy in a participant that received IP is not considered an SAE unless it is suspected that the IP interacted with a contraceptive method and led to the pregnancy)

- is an important medical event

NOTE: Medical and scientific judgment should be exercised in deciding whether it is appropriate to consider other situations serious, such as important medical events that may not be immediately life-threatening or result in death or hospitalization but may jeopardize the patient or may require intervention to prevent one of the other outcomes listed in the definition above. Examples of such events are intensive treatment in an emergency room or at home for allergic bronchospasm, blood dyscrasias, or convulsions.

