### **9.5.3 Study Halting Criteria**

Any of the following criteria will trigger a review by the DSMB and a potential halt in IP administration or enrollment of new participants:

- Any participant death or SAE in which there a reasonable possibility that the IP caused the death or SAE, as judged by the investigator.

[Section 14.6](#) describes procedures in the event of suspension or termination of the study for all participants. The DSMB charter will include details of the procedures they will follow when reviewing study data (see [Section 12](#)).

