### **11.2. Event Assessment and Follow-up of Adverse Events**

The occurrence of an AE or SAE may come to the attention of study personnel during hospitalization and at outpatient visits or via telephone.

All AEs will be captured on the appropriate case report form (CRF). Information to be collected includes event description, time of onset, clinician's assessment of severity, relationship to IP (assessed only by those with the training and authority to make a diagnosis), and time of resolution/stabilization of the event. All AEs occurring while on study must be documented appropriately regardless of relationship. All AEs will be followed to adequate resolution.

Site staff will record all reportable events with start dates occurring any time after informed consent is obtained through Day 60. At each study visit, the investigator will inquire about the occurrence of AE/SAEs since the last visit. Events will be followed for outcome information until resolution or stabilization.

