### **11.3. Special Considerations**

#### **11.3.1 Adverse Events of Special Interest**

Investigators should specifically monitor several AEs potentially associated with varespladib treatment, including cerebrovascular accident (CVA; stroke), myocardial infarction (MI), and malignant cardiac arrhythmias. These AEs may also be associated with COVID-19. Investigators should carefully determine whether these AEs are potentially related to study drug.

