9.1.2. Deaths and Serious Adverse Events

Any deaths that occur during the study will be listed.

SAEs will be listed and also tabulated by system organ class and preferred term and presented by treatment.

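### The SAE note exempts admissions for diagnostic work-up of an AE, so some unplanned hospitalizations after dosing can miss SAE reporting, the SAE table and the DSMB trigger

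*Protocol*

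**What the plan says.** **Seriousness.** Protocol 11.1.3 opens broadly: "A serious adverse event (SAE) is any untoward medical occurrence that" meets one of the listed criteria. One criterion is that the event "requires inpatient hospitalization or prolongation of existing hospitalization". The note under that criterion makes two exemptions. The first covers elective admissions for conditions that predate exposure. The second states that "a hospital admission for a diagnostic evaluation of an AE, does not qualify the condition or event as an SAE". The remaining criteria (death, threat to life, disability, congenital anomaly, important medical event) stand without this qualification.

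**What depends on SAE status.** Protocol 11.2.5.1 requires a report within 24 hours for SAEs. Protocol 9.5.3 triggers a DSMB review for "Any participant death or SAE in which there a reasonable possibility that the IP caused the death or SAE", as judged by the investigator. SAP 9.1.2 says that "SAEs will be listed and also tabulated by system organ class and preferred term and presented by treatment".

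**COVID-19 worsening.** Protocol 11.1.1 says that worsening of the disease under study "will not automatically be considered an AE unless the investigator believes that the progression is related to study drug". Protocol 11.2 says: "All AEs occurring while on study must be documented appropriately regardless of relationship". Protocol 11.2.1 adds that clinically relevant observations made at a visit also count as AEs, with no exception for COVID-19. SAP 6.1.7 identifies organ failure, including respiratory failure, from the terms of reported AEs.

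**The concern.** The elective-admission exemption is harmless, because such an admission is planned and concerns a condition that was there before the drug. The diagnostic exemption beside it is different in kind: it concerns an AE, and an admission to investigate one is normally unplanned. Under Protocol 9.6 participants may be discharged during dosing with their remaining tablets, and under 11.2 events are collected to Day 60. Readmission is therefore one of the main ways in which a later event becomes serious.

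Protocol 11.3.1 asks investigators to watch for events "including cerebrovascular accident (CVA; stroke), myocardial infarction (MI), and malignant cardiac arrhythmias". Suspected events of this kind may first come in as admissions for work-up. Whether one counts as serious would then turn on how the purpose of the admission is described, or on a judgment that another criterion applies.

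Safety is part of the primary objective, and the incidence of serious AEs is a named safety endpoint. A definition that leaves out some hospitalizations affects individual reporting as well as the by-arm SAE count.

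The rule on COVID-19 worsening raises a smaller question. It asks for a causality judgment before an event is recorded, whereas 11.2 asks for recording first and causality afterwards.

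**Working it through.** The documents state no figure on this point, so the check is a trace through the text, followed by a rough size on assumed rates.

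**1. An AE admitted for work-up that meets no other seriousness criterion**

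| Step | Source | Result as written |
|---|---|---|
| Recorded as an AE | Protocol 11.2 | Yes |
| In the TEAE tables | SAP 6.1.7 and 9.1 | Yes, if onset is before 30 days after the last dose |
| In the Part 2 by-arm AE comparison to Day 60 | SAP 9.1 | Yes, if above mild or related |
| Classed as an SAE | Protocol 11.1.3 note | No |
| 24-hour report | Protocol 11.2.5.1 | No |
| SAE table and listing | SAP 9.1.2 | No |
| DSMB trigger, if thought drug-related | Protocol 9.5.3 | No |

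The last dose falls on Day 7 or Day 8, so the SAP's TEAE window closes at about Day 37 (7 + 30) or Day 38 (8 + 30). SAP 9.1.2 does not limit the SAE table to treatment-emergent events. For onsets from then to Day 60, an event not classed as serious therefore appears only in the AE listings and, in Part 2, in the Day 60 comparison.

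**2. Rough size**

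Assumptions, neither taken from the documents: 5-15% of participants are readmitted, and half of those admissions are for evaluation.

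- Part 2, 72 participants: 72 × 0.05 × 0.5 = 1.8; 72 × 0.15 × 0.5 = 5.4.
- Part 1, 18 participants: 18 × 0.05 × 0.5 = 0.45; 18 × 0.15 × 0.5 = 1.35.

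These are upper figures, because some of the events will be serious on another criterion. SAP Section 10 reports that only one Part 2 participant had been recruited at the pause, so the Part 2 figure applies only if enrollment resumes.

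**3. COVID-19 worsening**

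- Protocol 11.1.1 does not require it to be recorded as an AE unless the investigator believes it drug-related. The same paragraph says that worsening of a pre-existing condition is an AE.
- Protocol 11.2 and 11.2.1 point the other way, so two sites could record the same event differently and each follow the protocol.
- Take a survivor who is intubated for COVID-19 progression not believed drug-related, with no AE entered. SAP 6.1.7 and 8.2.3 count that participant as a respiratory failure from the support used. SAP 8.2.9, which relies on the AE-based definition in 6.1.7, could score all 28 days as free of organ failure.
- SAP 8.2.9 treats all days as organ failure for participants who die, so the undercount is confined to survivors.

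**4. What the DSMB sees**

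Protocol Section 12 speaks of safety results and unblinded safety data. The Synopsis, Protocol 9.7 and SAP 4.2 speak of Part 1 results that include safety data, and SAP 4.2 speaks of unblinded data in Part 2. The text does not settle whether by-arm respiratory failure is in the reports. The charter is not among the documents.

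**The case against.** The best reply is that little is lost. The note removes only the diagnostic admission as a ground for seriousness. A confirmed stroke or infarction that needs inpatient treatment is no longer an admission for evaluation alone, and it may be life-threatening, disabling or an important medical event. Cerebrovascular accident, acute coronary syndrome and serious arrhythmias are also named in the dose-holding criteria of 9.5.1, so they will be noticed. This stands, and it limits the gap to work-up admissions that meet no other criterion. It does not close the gap. The important-medical-event criterion is a judgment, and the note takes away the objective criterion that would make the judgment unnecessary.

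A reader might infer that these events disappear from the safety tables. They do not: they remain AEs and appear in the AE outputs set out above.

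A reader might also infer that the COVID-19 rule hides a harm signal, or disables the DSMB trigger. The documents support neither.

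- Respiratory failure and death are compared by arm whatever their believed cause (SAP 8.1, 8.2.2, 8.2.3), alongside WHO score and ventilator, ICU and oxygen days. SAP Section 10 now also gives summary statistics and confidence intervals for these outcomes in Part 1. A loss of power calculated on AE records alone would not measure lost evidence.
- The trigger in 9.5.3 itself requires a reasonable possibility of causation, so worsening judged unrelated would not set it off even if recorded as an SAE. Only a narrow gap remains, where causation is thought possible but not believed.

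Keeping disease progression out of the AE data when it is an efficacy outcome is a defensible choice. What remains is the conflict between sections and its effect on an endpoint built from AEs.

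**Conclusion.** The main point holds. As written, 11.1.3 lets an unplanned post-dose hospitalization for work-up of an AE be non-serious when no other criterion applies. That event then misses the 24-hour report, the SAE table and, if thought drug-related, the DSMB trigger. The number affected is probably small: about 2 to 5 at most in 72 participants and about 0 to 1 in 18, on the assumed rates. The case for the change rests on the wording and its low cost, not on those figures.

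The second point is one of consistency. Protocol 11.1.1 conflicts with 11.2 and 11.2.1. Because SAP 6.1.7 relies on reported AEs, organ failure in survivors can be undercounted and organ failure-free days overstated. The effect on the difference between arms cannot be determined from the documents.

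**What to change.** 1. In the note to Protocol 11.1.3, delete the exemption for admissions for diagnostic evaluation and keep the one for elective admissions. The cost is one clause and a few more SAE forms.

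2. Reconcile Protocol 11.1.1 with 11.2 and 11.2.1, so that all sites record COVID-19 worsening in the same way. If it is to stay outside the AE data, derive respiratory organ failure in SAP 6.1.7 from the respiratory support data already collected, or state that the endpoint counts only organ failure reported as an AE.

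3. Confirm in the DSMB charter or report template that the by-arm respiratory failure and death outcomes planned in SAP 8.1 and 8.2 are included. This needs no new data.

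SAP Section 10 already foresees a protocol and SAP amendment for Part 2, which could carry items 1 and 2. For Part 1, the healthcare encounters documented to Day 60 under Protocol 10.3.1.3 allow a check of 18 participants for unplanned readmissions whose AE was not classed as serious. Any found can be noted in the study report.

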#### **11.1.4 Treatment-emergent Adverse Events**

An AE is defined as treatment-emergent if the first onset or worsening is after the first administration of IP and within the study's AE reporting period.

### **11.2. Event Assessment and Follow-up of Adverse Events**

The occurrence of an AE or SAE may come to the attention of study personnel during hospitalization and at outpatient visits or via telephone.

All AEs will be captured on the appropriate case report form (CRF). Information to be collected includes event description, time of onset, clinician's assessment of severity, relationship to IP (assessed only by those with the training and authority to make a diagnosis), and time of resolution/stabilization of the event. All AEs occurring while on study must be documented appropriately regardless of relationship. All AEs will be followed to adequate resolution.

Site staff will record all reportable events with start dates occurring any time after informed consent is obtained through Day 60. At each study visit, the investigator will inquire about the occurrence of AE/SAEs since the last visit. Events will be followed for outcome information until resolution or stabilization.

#### **11.2.1 Assessment**

The investigator is responsible for the detection and documentation of events meeting the criteria and definition of an AE or SAE described previously. During hospitalization and at each outpatient visit or telephone visit, the participant will be allowed time to spontaneously report any issues since the last visit or evaluation. The investigator will then monitor and/or ask about or evaluate AEs using nonleading questions, such as

- “How are you feeling?”
- “Have you experienced any issues since your last visit?”
- “Have you taken any new medications since your last visit?”

Any clinically relevant observations made during the visit will also be considered AEs.

#### **11.2.2 Evaluation**

##### **11.2.2.1 Severity of Adverse Events**

The clinical severity of an AE will be classified by the investigator using the National Cancer Institute (NCI) Common Terminology Criteria for Adverse Events (CTCAE) v5.0. Specific conditions and symptoms have values or descriptive comments for each grade. The CTCAE grades are based on this general guideline:

---

Grade 1	Mild; asymptomatic or mild symptoms; clinical or diagnostic observations only; intervention not indicated.
Grade 2	Moderate; minimal, local or noninvasive intervention indicated; limiting age-appropriate instrumental activities of daily living.
Grade 3	Severe or medically significant but not immediately life-threatening; hospitalization or prolongation of hospitalization indicated; disabling; limiting self-care activities of daily living.
Grade 4	Life-threatening consequences; urgent intervention indicated.
Grade 5	Death related to AE.

Changes in the severity of an AE will be documented.

It is important to distinguish between severe AEs and SAEs. Severity is a classification of intensity whereas an SAE is an AE that meets serious criteria, as described in [Section 11.1.3](#).

#### **11.2.2.2 Seriousness**

The investigator is to evaluate whether the AE meets serious criteria, as described in [Section 11.1.3](#).

#### **11.2.2.3 Action(s) Taken**

Action(s) taken may consist of:

IP interrupted	IP schedule was modified by temporarily terminating the prescribed regimen of IP.
IP withdrawn	IP schedule was modified through termination of IP.

#### **11.2.2.4 Outcome at the Time of Last Observation**

The outcome at the time of last observation will be classified as:

- Recovered/resolved
- Recovered/resolved with sequelae
- Recovering/resolving
- Not recovered/not resolved
- Fatal\*
- Unknown

\*Only select fatal as an outcome when the AE results in death. If more than one AE is judged to be possibly related to the participant's death, the outcome of death should be indicated for each such AE.

### 11.2.2.5 Adverse Event Relationship to Investigational Product

The investigator must assess each AE's relationship to the IP. Infection with SARS-CoV-2 resulting in severe COVID-19 is associated with broad, complex, and significant pathophysiology. The Investigator should carefully consider the list of possible manifestations of COVID-19 when assigning a relationship of specific AEs to the study drug. The categories for classifying the investigator's opinion of the relationship are as follows:

The investigator must assess each AE's relationship to the IP. The categories for classifying the investigator's opinion of the relationship are as follows:

Definitely	A definite probability exists of a relationship between the AE and IP.
Probably	A reasonable probability exists of a relationship between the AE and IP.
Possibly	A possibility exists of a relationship between the AE and IP.
Unrelated	No reasonable possibility exists of a relationship between the AE and IP.

### 11.2.3 Documentation

All AEs that occur within the period of observation for the study must be documented in the CRF with the following information, where appropriate. (The period of observation for the study is described in [Section 11.2](#).)

- AE name or term
- When the AE first occurred (start date and time)
- When the AE stopped (stop date and time or an indication of “ongoing”)
- Severity of the AE
- Seriousness (hospitalization, death, etc.)
- Actions taken
- Outcome
- Investigator opinion regarding the AE relationship to the IP

